longitudinal mediation model will allow for the determination of how drug condition and baseline estradiol, AEA and 2-AG levels affects subjective anxiety across session time, which mediates changes in heart rate, blood pressure and salivary cortisol across session time. I hypothesize THC-induced increases in subjective anxiety mediate increases in heart rate, blood pressure and salivary cortisol across session time.

Significance.

The goal of this project is to determine the influence of estradiol and endocannabinoids on THC-induced increases in subjective anxiety and how this may mediate increases in heart rate, blood pressure and salivary cortisol. Cannabis and THC accessibility and consumption are increasing as medical and recreational use is being legalized across more states. Although there is evidence both low doses of cannabis and oral THC have some therapeutic effects, such as anxiolytic, analgesic and hunger stimulating effects, at moderate and higher doses the drugs can also produce serious unwanted effects including anxiety and paranoia (Zeiger et al., 2010; Crean et al., 2011). THC's effects vary across individuals, and may depend in part on body mass index, age, frequency of cannabis use and other variables such as hormone or endogenous cannabinoid levels (Wiley et al. 2014, D'Souza et al. 2008, Pope et al. 1996). Uninformed use of the substance could pose a public health risk, especially as recreational use is on the rise. A better understanding of individual differences in acute responses to THC will help to maximize the potential benefits and minimize adverse consequences of THC and cannabis-related products.

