For this study we will use a mixed within- and between subject design to examine effects of THC (0 and 15 mg) in two groups of female occasional cannabis users: women tested in the early follicular phase of their menstrual cycle (EFG; N=30) and women tested in the late follicular phase (LFG; N=30). Occasional cannabis users will be defined as individuals who have used cannabis 10 or less occasions in the past thirty days. Females will be randomly assigned EFG or LFG groups. EFG women will be tested 1 to 8 days since the first day of menstruation and LFG women between days 9 and 14. Subjects will attend two four-hour experimental sessions in which they receive THC (15 mg THC) or placebo in counterbalanced order under double blind conditions. Plasma and saliva samples will be obtained before capsule consumption at the start of each session for baseline hormone, endocannabinoid and cortisol levels. The primary outcome measure is salivary cortisol, which will be measured both at baseline and periodically post-drug consumption. Secondary outcome measures include heart rate, blood pressure, body temperature, subjective drug effects (i.e. "feel drug effect"), and THC-induced anxiety. For Aim 1 we will examine THC-induced increases in cortisol in relation to baseline estradiol levels. For Aim 2 will examine THC-induced cortisol in relation to baseline endocannabinoid levels. For Aim 3 we will examine THC-induced increases in heart rate and subjective drug effects relative to THC-

induced increases in cortisol. The study will be approved by the Institutional Review Board at the University of Chicago, in accordance with the Code of Federal Regulations (Title 45, Part 46) adopted by the National Institutes of Health and the Office for Protection from Research Risks of the US Federal Government. The studies will be conducted in accordance with the Helsinki Declaration of 1964 (revised 1989) and the National Advisory Council on Drug Abuse Recommended Guidelines for the Administration of Drugs to Human Subjects.

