4. *The Drug Effects Questionnaire* (DEQ, Johanson and Uhlenhuth, 1980; Morean et al. 2013): This questionnaire contains visual analogue scales measuring subjective drug effects. It contains five questions, each associated with an anchored 100 mm line, on which participants indicate their response: "Do you feel any drug effect?" (rated from "none at all" to "a lot"), "Do you like the effects you are feeling now?" (rated from "not at all" to "very much"), "Do you dislike the effects you are feeling now?" (rated from "not at all" to "very much") "Are you high?" (rated from "not at all" to "very much") and "Would you like more of what you consumed, right now?" (rated from "not at all" to "very much"). This measure will be used another manipulation check to ensure the drug produced drug effects, but it will not be specific to a certain drug class.

5. *The Profile of Mood States* (POMS, McNair et al., 1971): This scale consists of 72 adjectives commonly used to describe momentary mood states. Participants indicate how they feel in relation to each of the 72 adjectives on a 5-point scale from "not at all" (0) to "extremely" (4). The questionnaire is comprised of eight subscales (Anxiety, Depression, Anger, Vigor, Fatigue, Confusion, Friendliness, Elation). Two summary scales are derived from the other scales: Arousal = (Anxiety + Vigor) - (Fatigue + Confusion); Positive Mood = Elation – Depression. This measure will be used to examine changes in state anxiety pre- and post-drug consumption.

Time	Activities	Measures
------	------------	----------

12:00 pm	Arrive, urine, and breath tests	Drug and pregnancy tests, breathalyzer
12:15 pm	Time point (baseline), saliva sample and blood draw	Subjective measures, HR, BP, Temp., saliva sample and blood draw
12:30 pm	Capsule (0, 15 mg THC)	
1:00 pm	Time point	Set up ECG, subjective reports, HR, BP, Temp.
1:30 pm	Time point	Saliva sample, subjective reports, HR, BP, Temp.
2:00 pm	Time point	Saliva sample, subjective reports, HR, BP, Temp.
2:30 pm	Time point	Saliva sample, subjective reports, HR, BP, Temp., EEfRT
3:00 pm	Time point	Saliva sample, subjective reports, HR, BP, Temp.
4:00 pm	Departure	End of session questionnaire, removal of electrodes

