Side effects: The drugs used in this study may produce a number of side effects, although most people do not experience any problems at the doses used in this study. Side effects may include abdominal pain, nausea, vomiting, dizziness, feelings of wellbeing, paranoia, sleepiness, abnormal thinking.

Driving or operating machinery: There may be risks to participants if they decided to drive, bike or operate machinery after the session. Therefore, they will not be allowed to drive or bike themselves to the session.

Confidentiality: There may be a risk of loss of confidentiality concerning some of the personal information participants provide to the investigators. As with any study, we will take many precautions to protect participant confidentiality.

Saliva Sample Protocol and Analysis Saliva samples for cortisol analysis will be obtained pre-drug consumption and 1, 1.5, 2, and 2.5 hours post-drug consumption by unstimulated passive drool. Participants will tilt their head forward, allowing the saliva to pool on the floor of their mouth, and then pass the saliva

through the SalivaBio Collection Aid (SCA) into a polypropylene vial. Levels of cortisol in saliva will be measured using a salivary cortisol ELISA kit, a competitive immunoassay specifically designed and validated for the quantitative measurement of salivary cortisol, at the University of Chicago Clinical Research Center.

Plasma Sample Protocol and Analysis

Ovarian Hormone Analysis 5ml blood draws will be obtained while participants are seated and collected in BDVacutainer Gold Top Serum tubes. Samples will be centrifuged at least 30 minutes after collection. The top layer of serum will be collected, aliquoted, and frozen at -80 °C until analyses for hormone levels occur. Plasma estradiol levels will be measured using an ELISA Estradiol (E2) assay. Plasma progesterone levels were measured using the Coat-a-Count Progesterone procedure (Diagnostic Products Corporation).

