Statistical Analyses Sample Size Calculation: Sample size calculations were conducted using G*Power3.1 Software. Since there are no published data on effects of estradiol or eCB levels on response to THC a small effect size was assumed ($d = 0.3$). Recruiting 30 participants for each experimental group, 30 females in early follicular phase, 30 females in late follicular phase, for this study will allow for 80% power to detect an effect at alpha level $p = 0.05$.

A multilevel longitudinal mediation model will be used to analyze the collected data. Our independent variables include within-subjects drug dose and between subjects estradiol (EFG or LFG), AEA and 2-AG levels. Our mediator variable is subjective anxiety across session time. Our dependent outcome measures include heart rate, blood pressure and salivary cortisol across session time. A multilevel longitudinal mediation model will allow for the determination of how drug condition and baseline estradiol, AEA and 2-AG levels affects subjective anxiety across session time, which mediates changes in heart rate, blood pressure and salivary cortisol.

Expected Outcomes Based on several preclinical studies, I expect the LFG to have higher levels of estradiol and anandamide at baseline than the EFG, but no significant differences in baseline trait anxiety, anxiety sensitivity or salivary cortisol (Reed and Carr, 2000; Gorzalka and Dang, 2012; Monero-Lopez et al. 2018). Further, I expect that the effect of THC on subjective anxiety, heart rate and salivary cortisol will be greater in the LFG compared to the EFG, even after including any possible baseline differences in cortisol, trait anxiety or endocannabinoids as a covariate. Additionally, based on preliminary data and prior literature, I expect females with lower endocannabinoid levels, after controlling for cycle phase or estradiol levels, to experience larger increases in subjective anxiety, heart rate and report significantly greater subjective drug and mood effects of oral THC in a dose dependent manner (Hill et al. 2010). Finally, I expect THC-induced change in cortisol to mediate the increase in heart rate and greater subjective drug and mood effects. These results will contribute significantly to the small literature on individual differences in response to THC and lay a foundation for future

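### Aim 3 gives anxiety and cortisol no temporal order and elsewhere reverses the path, so the planned mediation model cannot support a directional conclusion

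*Combined protocol and SAP*

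**What the plan says.** The Statistical Analyses section describes one model, a multilevel longitudinal mediation model. On the mediator it says "Our mediator variable is subjective anxiety across session time", and on the outcomes "Our dependent outcome measures include heart rate, blood pressure and salivary cortisol across session time". Aim 3 uses the same construction, with anxiety as the variable "which mediates changes in heart rate, blood pressure and salivary cortisol across session time", and gives the hypothesis as "I hypothesize THC-induced increases in subjective anxiety mediate increases in heart rate, blood pressure and salivary cortisol across session time". None of these places states a lag, an order between mediator and outcome, or an adjustment for earlier cortisol.

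Two other places point the opposite way. Expected Outcomes says "I expect THC-induced change in cortisol to mediate the increase in heart rate and greater subjective drug and mood effects". The Approach section says "For Aim 3 we will examine THC-induced increases in heart rate and subjective drug effects relative to THC", and the sentence ends by naming the THC-induced cortisol increase. The Approach section also makes salivary cortisol the primary outcome.

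On timing, Saliva Sample Protocol and Analysis places the samples "pre-drug consumption and 1, 1.5, 2, and 2.5 hours post-drug consumption". The session timetable agrees. Its 1:00 pm row reads "Set up ECG, subjective reports, HR, BP, Temp" and has no saliva sample; the rows from 1:30 to 3:00 pm have both saliva and subjective reports.

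**The concern.** Mediation is a claim about order: the mediator has to move before the outcome. If anxiety and cortisol are taken from the same clock time, the fitted path is a concurrent association. It would look much the same if anxiety raised cortisol, if cortisol raised anxiety, or if both followed the THC time course.

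This affects the primary outcome in the only model that the plan describes. Because the documents state both directions and fix no pairing, direction and lag could also be chosen after the data are seen. Aim 3 could then report a path that is not there or miss one that is.

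**Working it through.** **The plan's own figure.** There is none for Aim 3. The only statistical figure is 80% power with 30 per group and d = 0.3. It names no test and does not address a mediated path, and nothing below depends on it.

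**Direction, side by side.** Aim 3 and Statistical Analyses: THC, then anxiety, then heart rate, blood pressure and cortisol. Expected Outcomes: THC, then cortisol, then heart rate and subjective drug and mood effects. Approach: heart rate and subjective effects examined relative to cortisol. The second and third do not name anxiety on its own, but they put cortisol where Aim 3 puts anxiety.

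**What the timetable allows.** The capsule is given at 12:30 pm.
- Saliva: 12:15, 1:30, 2:00, 2:30, 3:00.
- Subjective reports: 12:15, 1:00, 1:30, 2:00, 2:30, 3:00.
- Post-dose saliva samples with a report 30 minutes earlier: 4 of 4. With one at the same time: 4 of 4.
- Lagged pairs: 4 x 2 sessions x 60 women = 480. Same-time pairs: 480 post-dose, or 5 x 2 x 60 = 600 with baseline.
- Reverse lag (cortisol 30 minutes before anxiety): 3 x 2 x 60 = 360, because no saliva is taken at 1:00 pm.

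**Effect of the pairing if anxiety acts on cortisol after a delay.** All inputs here are assumptions. Let cortisol at time t equal 0.40 x anxiety at t - d plus noise, in SD units. Let the correlation between anxiety scores u minutes apart be rho^(u/30), with rho = 0.3, 0.5 or 0.7. A regression on anxiety measured L minutes before the sample then has slope

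0.40 x rho^(|d - L|/30), with L = 0 (same time) or L = 30 (lagged).

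| True delay d | Same-time slope (rho 0.3 / 0.5 / 0.7) | Lagged slope (rho 0.3 / 0.5 / 0.7) |
|---|---|---|
| 0 min | 0.40 / 0.40 / 0.40 | 0.12 / 0.20 / 0.28 |
| 15 min | 0.22 / 0.28 / 0.33 | 0.22 / 0.28 / 0.33 |
| 30 min | 0.12 / 0.20 / 0.28 | 0.40 / 0.40 / 0.40 |
| 40 min | 0.08 / 0.16 / 0.25 | 0.27 / 0.32 / 0.36 |

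For example, at d = 40 and rho = 0.3, same-time pairing gives 0.40 x 0.3^(40/30) = 0.08 and the lagged score gives 0.40 x 0.3^(10/30) = 0.27. The two pairings tie at 15 minutes, and the lag is better only beyond that.

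**Simulation at the trial's size.** 60 women, two sessions, 400 runs per scenario; within-person regression of post-dose cortisol on anxiety, adjusted for drug, time and drug-by-time, with cluster-robust standard errors. Effect sizes, autocorrelations and the THC time profile are assumed. Monte Carlo error is at most about 2.5 percentage points.

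| Scenario | Same-time: mean slope, rejection | Lagged: mean slope, rejection |
|---|---|---|
| True 30-minute effect 0.20, autocorrelation 0.2 / 0.4 / 0.6 / 0.8 | 0.03 / 0.07 / 0.10 / 0.15; 10 / 22 / 35 / 53% | about 0.20 throughout; 98 / 96 / 90 / 80% |
| No effect, shared drug driver | 0.035; 10% | 0.030; 10% |
| No effect, shared drug driver plus shared momentary driver | 0.24; 99.5% | 0.00; 7.5% |
| True 30-minute effect 0.20, both shared drivers | 0.30; 99.8% | 0.20; 96.5% |
| Only cortisol acts on later anxiety, 0.20 | 0.07; 25% | 0.02; 6.5% |

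The first row shows dilution, the third and fourth inflation, and the last a reversed path read as anxiety-to-cortisol in a quarter of runs. The lagged model here did not include the preceding cortisol value, so the runs compare pairings and do not test the full model proposed below.

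**The case against.** The strongest reply is that the plan never says same-time pairing. A longitudinal multilevel model with variables over the session could carry lagged terms or trajectories. That stands: a reader might infer that the plan specifies a same-time model, but it is silent. Same-time pairing is only the natural reading of identical wording for mediator and outcome. The defect is that the timing is unspecified.

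A reader might also infer that the anxiety-to-cortisol path will be diluted by 30 to 70%. The documents do not support this. They give neither a cortisol response delay nor an autocorrelation for anxiety. That loss is simply 1 - rho for rho from 0.7 to 0.3, with the delay set to exactly 30 minutes. At 15 minutes the lag gains nothing; if the effect is concurrent, the lagged score takes the same loss; and a shared momentary driver inflates the same-time slope.

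Three further objections stand in part:
- A lag alone does not show direction. Earlier cortisol or an individual's THC time course could still produce a lagged association, as the 10% rejection under a shared drug driver shows for both pairings.
- The 30-minute spacing of anxiety scores is not assured. The text under Experimental Session Timeline allows questionnaires every 30 or 60 minutes. The timetable says only that subjective reports are taken, and either STAI or POMS could supply the mediator.
- Lagging has its own cost: the 3:00 pm anxiety score and the baseline pair drop out.

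None of these supplies the missing order or removes the contradiction over direction.

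**Conclusion.** The point holds as a gap and a contradiction in the plan. Aim 3 draws a directional conclusion from a model with no stated order, while Expected Outcomes states the reverse path and the Approach section leans the same way. Read as same-time pairing, the model cannot separate the competing explanations.

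The size and sign of the bias are unknown. Conditional on a true effect of 0.40 and rho from 0.3 to 0.7, same-time pairing recovers 0.22-0.33 at a 15-minute delay (the same as the lagged score), 0.12-0.28 at 30 minutes (lagged 0.40) and about 0.08-0.25 at 40 minutes (lagged 0.27-0.36). With shared drivers and no effect it gave 0.24. These values rest on assumed delays, correlations and drivers. That the order is missing, that the directions conflict and that the schedule permits an ordered analysis follow from the documents alone, provided that the timetable's subjective reports include the chosen anxiety scale each time.

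**What to change.** 1. Choose one direction for Aim 3 and reconcile Aim 3, Approach, Statistical Analyses and Expected Outcomes to it.
2. Name one anxiety scale (STAI or POMS) as the mediator, state that it is given at every timetable point, and align the 30-or-60-minute wording with the timetable.
3. If anxiety stays the mediator, prespecify for cortisol the score 30 minutes before each saliva sample: 1:00 with 1:30, 1:30 with 2:00, 2:00 with 2:30, 2:30 with 3:00. Adjust for the preceding cortisol sample (for 1:30 pm this is the 12:15 pm baseline, 75 minutes earlier), baseline anxiety, drug, time and drug-by-time.
4. Report the same-time model and the reverse lag (three pairs per session) alongside it.
5. Describe same-time results, including those for heart rate and blood pressure, as associations.
6. Give any dilution figure only as conditional on a stated delay.

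The cost is plan wording and a little more analysis, with no extra visits or samples. The lagged model uses 480 pairs against 600 same-time pairs with baseline, leaves the 3:00 pm anxiety score unused, and is itself diluted if the effect is in fact concurrent. That last risk is a reason to show both models.

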Aim 1: To examine whether high levels of estradiol augment the effect of THC on subjective anxiety, heart rate, blood pressure and salivary cortisol in females. To test this, female occasional cannabis users will receive a single dose of THC (0, 15 mg) during either the early follicular phase (days 1-8) when estradiol levels are low, or during the late follicular phase (days 9-14) when estradiol levels are high. Participants will attend two experimental sessions separated by at least four days, to allow for clearance of the drug. Plasma levels of estradiol, progesterone, and endocannabinoids, as well as salivary cortisol, physiological measures and subjective mood ratings will be obtained at the beginning of all three sessions. During the sessions, physiological measures, subjective ratings of drug effects and mood, and salivary cortisol will be obtained at regular intervals after drug consumption. I hypothesize THC will produce a greater increase in subjective anxiety, heart rate, blood pressure and salivary cortisol during the late follicular phase, and that this will be correlated with higher circulating levels of estradiol.

Aim 2: To examine whether low levels of circulating endocannabinoids augment the effects of THC on subjective anxiety, heart rate, blood pressure and salivary cortisol in females. To test this, the plasma samples mentioned above will also be analyzed for endocannabinoids, anandamide (AEA) and 2-arachidonoylglycerol (2-AG) levels. Baseline AEA and 2-AG levels will be compared to THC-induced increases in subjective anxiety, heart rate, blood pressure and salivary cortisol. I hypothesize females with lower endocannabinoid levels will exhibit greater THC-induced increases in subjective anxiety, heart rate, blood pressure and salivary cortisol levels.

Aim 3: To evaluate determine whether subjective anxiety mediates the physiological stress response after THC. To test this, I will use a multilevel longitudinal mediation model to analyze the collected data. Our independent variables will include within-subjects drug dose and between subjects estradiol (EFG or LFG), AEA and 2-AG levels. Our mediator variable will be subjective anxiety across session time. Our dependent outcome measures include heart rate, blood pressure and salivary cortisol across session time. A multilevel

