Participants 60 healthy female volunteers who are occasional cannabis users (18-35 years, <11 uses of cannabis in past month) will be recruited by posters, advertisements, and word-of-mouth referrals, without regard to race or ethnicity. An undergraduate from the University of Chicago college will only be considered as a potential participant if she is within their 4th year of study. Potential participants will undergo a semi-structured clinical psychiatric interview (American Psychiatric Association, 2013) and provide information about current and lifetime history of drug use. Individuals taking any medications, or with serious psychiatric disorders such as psychosis or severe Post-Traumatic Stress Disorder or Obsessive Compulsive Disorder will be excluded. We will also exclude individuals with moderate or severe Substance Use Disorder, and those with BMI outside the normal range (less than 19 or more than 26), abnormal EKG, or pregnant or planning to be pregnant. Participants must have regular menstrual cycles and not be lactating or using hormonal contraceptives. Participant selection will be monitored throughout the study to ensure that the two groups, EFG and LFG, are matched on demographic characteristics, including age, race, education, SES, smoking, drinking, and drug use. Participants will be paid a \$180 for completing all sessions. They will also have the opportunity to win an additional \$8-\$35 based on experimental task performance.

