Orientation Session Participants will first participate in a 1-hour orientation session to provide informed consent, agree to the study conditions described above, complete the Trait Anxiety Inventory (Spielberger et al. 1971) and the Anxiety Sensitivity Inventory (Reiss et al. 1986), and practice questionnaires that will be administered throughout the sessions. Participants will be instructed to refrain from any use of drugs or alcohol for 24 before the experimental sessions. They will be advised that they must pass urine tests on the days of their experimental sessions for recent drug use including cannabis, and to pass these tests they should abstain from use for one week if they are light users (1-2 times per week) and for two weeks if they are heavier users (e.g., every other day). They will be told to have a normal night's sleep before the session and abstain from eating for at least 6 hours prior to their session. For blinding purposes, subjects will be told the capsules used in the study may contain a placebo, stimulant, cannabinoid-like drug, or sedative. The reason for blinding is we wish to study the pharmacological effects of this drug, without the possible confound of expectancies. We and others have shown that expectancies influence responses to drugs, in ways that might obscure true biological differences in the effects of the drug (see Mitchell et al. 1996; Kirk et al. 1998; Metrik et al. 2009; Heinz et al. 2013). Subjects will then practice the physiological measures and subjective questionnaires.

Experimental Session Timeline Participants will attend two experimental sessions lasting from 12:00 pm to 4:00 pm. Sessions are run from 12:00 pm to 4:00 pm to account for the diurnal rhythm of salivary cortisol—levels reach lowest levels at around midnight, start to rise at around 2:00 am to 3:00 am, reach a peak at around 8:30 am, and then slowly decrease back down to complete the cycle over 24 hours (Debono et al. 2009). Females in EFG will participate 1-8 days after first day of menstruation, at a time when both estradiol and progesterone levels are low (Barbieri et al. 2014). Females in the LFG will participate 9-14 days after first day of menstruation, at a time when estradiol levels are peaking or have just peaked, but progesterone levels remain low. The half-life of oral THC in infrequent users is about 1.3 days (Smith-Kielland et al. 1999). Therefore sessions will be scheduled with a minimum of 4 days to allow for washout.

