sex-specific cannabis use guidelines, to prevent against THC-induced anxiety, paranoia, and psychosis, and new sex-specific cannabis use disorder treatment options.

Potential problems, Alternative strategies, and Limitations Several problems could arise. First, it may be difficult to recruit qualifying participants in the planned time frame. This seems unlikely since similar inclusion criteria have been used in prior studies within the lab and there has not been significant difficulty recruiting these individuals. But if this is the case, I will increase venues for advertising and identify new online recruitment sources. Second, the differences in responses to THC in females at different phases of their menstrual cycle may be too small to detect with this sample. This is possible, even though we based the sample size on a small effect size. If the findings look promising we would consider increasing our sample size or utilize the data as a pilot for a future study with a larger sample. Third, the two groups of females may differ in pre-capsule measures, such as mood states, cortisol levels, eCB levels, blood pressure or in demographic characteristics such as prior drug use. I will include any of these significant differences between groups as a covariate in the final analyses.

Literature Cited

American Psychiatric Association. (2013). Cautionary statement for forensic use of DSM-5. In *Diagnostic and statistical manual of mental disorders* (5th ed.). doi:10.1176/appi.books .9780890425596.744053

Craft, R. M., & Leitl, M. D. (2008). Gonadal hormone modulation of the behavioral effects of Δ9-tetrahydrocannabinol in male and female rats. *European Journal of Pharmacology*, 578(1), 37–42.

Crean, R. D., Crane, N. A., & Mason, B. J. (2011). An Evidence Based Review of Acute and Long-Term Effects of Cannabis Use on Executive Cognitive Functions. *Journal of Addiction Medicine*, 5(1), 1–8. <https://doi.org/10.1097/ADM.0b013e31820c23fa>

D'Souza, D. C., Ranganathan, M., Braley, G., Gueorguieva, R., Zimolo, Z., Cooper, T., ... Krystal, J. (2008). Blunted Psychotomimetic and Amnestic Effects of Δ-9-Tetrahydrocannabinol in Frequent Users of Cannabis. *Neuropsychopharmacology*, 33(10), 2505–2516. <https://doi.org/10.1038/sj.npp.1301643>

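### Aim 2 does not prespecify adjustment for cannabis use: it enters only if the two phase groups differ, a trigger that does not address confounding across AEA and 2-AG levels

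*Combined protocol and SAP*

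**What the plan says.** - **Aim 2.** The comparison is stated without covariates: "Baseline AEA and 2-AG levels will be compared to THC-induced increases in subjective anxiety, heart rate, blood pressure and salivary cortisol".
- **Statistical Analyses.** The model terms are listed as follows: "Our independent variables include within-subjects drug dose and between subjects estradiol (EFG or LFG), AEA and 2-AG levels". There is no term for cannabis use.
- **Expected Outcomes.** The only control named for the endocannabinoid hypothesis is phase or hormone level: "I expect females with lower endocannabinoid levels, after controlling for cycle phase or estradiol levels".
- **Significance.** The protocol itself treats use as a possible modifier: "THC's effects vary across individuals, and may depend in part on body mass index, age, frequency of cannabis use and other variables".
- **Participants.** Use is recorded at screening, where candidates "provide information about current and lifetime history of drug use". The early follicular group (EFG) and late follicular group (LFG) are to be matched on drug use, among other characteristics.
- **Potential problems, Alternative strategies, and Limitations.** Prior drug use is one of the characteristics on which the two groups might differ, and the rule is "I will include any of these significant differences between groups as a covariate in the final analyses".
- **Approach.** Eligible women have used cannabis on at most 10 occasions in the past 30 days, so use is capped but not constant.

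**The concern.** Randomisation protects the EFG/LFG contrast and the THC/placebo contrast. It does not protect a comparison of women with low and high AEA or 2-AG, because nobody is assigned an endocannabinoid level. By naming phase or estradiol as a control, the plan accepts that Aim 2 needs covariate adjustment. It leaves out a characteristic that it says may change the response to THC and that it already records.

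Both provisions that deal with drug use, the matching and the significant-difference rule, act between the phase groups. Use can have the same mean in EFG and LFG and still rise or fall with AEA within each group.

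At stake is the reading of Aim 2. If heavier users have higher endocannabinoids and a blunted response, an association appears in the hypothesised direction with no endocannabinoid effect behind it. If heavier users have lower endocannabinoids, a true effect is hidden or reversed.

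**Working it through.** The plan gives no figure for this point. Its one design figure (80% power, 30 per group, d = 0.3) is not an input here.

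**1. What the placebo session removes.** Let U be cannabis use, E baseline endocannabinoid level and D a woman's response under THC minus her response under placebo. Write the outcome as

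Y = μ + γU + drug × (δ + θU + βE) + error, with drug = 0 or 1.

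Then D = δ + θU + βE + error. The main effect γU cancels. The use-by-drug term θU (tolerance) does not, and this is the kind of dependence that the Significance section describes.

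**2. Induced correlation.** Let a = corr(U, E) and b = corr(U, D). If β = 0, then corr(E, D) = a × b. The documents give neither a nor b, so both are assumptions. The values below are absolute; their signs set the direction of the bias.

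**3. False-positive rate, adjusting for phase only.** N = 30 + 30 = 60, two-sided 5%. By Fisher's transformation with one covariate, λ = atanh(ab) × √(60 − 3 − 1) = atanh(ab) × 7.483, and the rate is P(Z > 1.96 − λ) + P(Z < −1.96 − λ).

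- 0.2/0.2: ab = 0.04, λ = 0.299, rate = 0.048 + 0.012 = 6.0%
- 0.3/0.3: ab = 0.09, λ = 0.675, rate = 0.099 + 0.004 = 10.4%
- 0.4/0.4: ab = 0.16, λ = 1.208, rate = 0.226 + 0.001 = 22.7%

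**4. Simulation of three analyses** (6,000 runs per setting, no true endocannabinoid effect). The middle column applies the plan's rule: use is added only when EFG and LFG differ on it at p < 0.05.

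| Assumed a / b (absolute) | Phase only | Plan's conditional rule | Use always included |
|---|---|---|---|
| 0 / 0.3 | 5.3% | 5.3% | 5.3% |
| 0.2 / 0.2 | 5.7% | 5.7% | 4.9% |
| 0.3 / 0.3 | 10.6% | 10.3% | 5.4% |
| 0.4 / 0.4 | 23.3% | 22.6% | 4.8% |

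The simulation agrees with step 3. The conditional rule fired in about 5% of runs, as a 5% test should between randomised groups, so it removed almost none of the inflation. Matching on drug use would be expected to make it fire less often.

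**5. Imperfect measurement of use.** The last column assumes that use is measured without error. If recorded use has reliability R, the correlation left after adjusting for it is ab(1 − R) / √[(1 − a²R)(1 − b²R)], and the multiplier becomes √(60 − 3 − 2) = 7.416. At 0.4/0.4:

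- R = 0.7: 0.16 × 0.3 / (1 − 0.16 × 0.7) = 0.048 / 0.888 = 0.054, rate about 6.9%
- R = 0.5: 0.16 × 0.5 / (1 − 0.16 × 0.5) = 0.080 / 0.920 = 0.087, rate about 9.9%

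A separate simulation gave 6.8% and 10.2%. Both reliabilities are assumptions. Adjustment removes most of the inflation, but not all of it.

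**The case against.** **The decisive link is missing.** Confounding needs use to be related to baseline AEA or 2-AG, and no section says that it is. This stands. A reader might infer that Aim 2 is biased, or that tolerance explains the expected result; the documents support only a possibility of unknown direction.

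**The design narrows use.** Use is capped at 10 occasions in 30 days, moderate or severe substance use disorder is excluded, and women with a positive drug screen are dismissed. Large correlations are therefore harder to assume, and at 0.2/0.2 the inflation is about one percentage point. This stands as a limit on size.

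**The plan does provide for adjustment.** A reader might infer that cannabis use is never adjusted for. That is too strong: the Limitations section brings in prior drug use if the groups differ. What remains is that the trigger looks at the wrong comparison for Aim 2.

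**Recency of use.** A reader might infer that time since last use varies by design, because women are told to "abstain from use for one week if they are light users (1-2 times per week) and for two weeks if they are heavier users". The heavier tier is illustrated as use every other day, about 15 occasions in 30 days, which exceeds the cap of 10. As illustrated, that tier is largely ineligible, so the advice is weak evidence.

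**Prediction or mechanism.** The opening section speaks of prediction and the Significance section of risk factors. On that reading an unadjusted association is a legitimate result. Aim 2, however, asks whether low endocannabinoids augment THC's effects, which calls for an adjusted estimate. Reporting both serves both readings.

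**Conclusion.** The point holds in a limited form. Adjustment for cannabis use is not prespecified for Aim 2, and the conditional rule that could bring it in does not address confounding across AEA and 2-AG levels. The consequence is possible, not demonstrated: about 6% false positives at 0.2/0.2, 10% at 0.3/0.3 and 23% at 0.4/0.4, against a nominal 5%. These rates rest on assumed correlations, one confounder, a linear relation and N = 60. They fall to 5% if use is unrelated either to endocannabinoid level or to THC response. A reader might infer that adding the covariate restores 5% in full; that is so only if use is measured without error. The documents also do not support the inference that BMI is an equally necessary covariate: it appears in the same sentence of the Significance section, but it is already restricted to 19 to 26 and is given no link to endocannabinoids. This is an inexpensive improvement worth making, not a flaw that invalidates Aim 2.

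**What to change.** In Statistical Analyses, state that the Aim 2 models for AEA and 2-AG include past-30-day cannabis occasions and their interaction with drug condition, whether or not EFG and LFG differ on use. Report the AEA and 2-AG estimates with and without these terms, so that readers can see how far they depend on use.

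Leave the significant-difference rule in the Limitations section in place. It also covers baseline cortisol, mood and blood pressure, and nothing here shows it to be harmful. BMI and days since last use can be optional sensitivity covariates.

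The cost is SAP wording plus one main-effect and one interaction term in the multilevel model (one degree of freedom out of 60 women in a difference-score analysis). Use history is already collected at screening, so the main change needs no new data. Days since last use, if wanted, may need one added question at check-in. The write-up should say that adjustment is partial because use is self-reported.
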